1 SYNOPSIS

Title: A Multicenter, Double-Blind, Randomized, Placebo-Controlled Parallel-Group Phase 2 Study Evaluating the Safety and Efficacy of OnabotulinumtoxinA X for the Treatment of Moderate to Severe Glabellar Lines	
Background and Rationale:	The purpose of this Phase 2 clinical study is to evaluate the safety and efficacy of onabotulinumtoxinA X formulation (hereafter called "OnabotA X"). [REDACTED]
Objective(s) and Endpoint(s):	
The objectives of this study are:
 
Efficacy: To compare the efficacy of OnabotA X with placebo for the treatment of glabellar lines (GL) in subjects with moderate to severe GL
 
Safety: To evaluate the safety of OnabotA X for the treatment of GL in subjects with moderate to severe GL
 
Primary efficacy endpoint:
 
 • Achievement of \geq 1-grade improvement from baseline on the Allergan Glabellar Line Severity Scale (AGLSS) according to investigator assessments at maximum contraction at Day 30 
Secondary efficacy endpoints:
 
 • Achievement of None or Mild on the investigator-rated AGLSS assessments at maximum contraction at Day 30 • Responses of Very satisfied or Mostly satisfied on satisfaction with treatment per the Facial Line Satisfaction Questionnaire (FLSQ[®]) follow-up version Item 5 at Day 60 • Achievement of \geq 14-point psychosocial impact improvement from baseline at Day 30 per the FLSQ Impact domain, among subjects with baseline scores \geq 14 points 
Safety will be assessed based upon:
 
 • Incidence of adverse events (AEs); [REDACTED]
Investigators:	Multicenter
Study Sites:	Up to 18 sites in the United States
Study Population and Number of Subjects to be Enrolled:	Approximately 280 subjects with moderate to severe GL; enrollment will be monitored to achieve an approximately balanced [REDACTED] distribution of subjects with investigator-assessed moderate or severe GL at maximum contraction at baseline.
Investigational Plan:	This is a 270-day, double-blind, randomized, placebo-controlled, Phase 2 study to assess the safety and efficacy of OnabotA X in adult subjects (\geq 18 years old) with moderate to severe GL. Eligible subjects will be randomized in a 2:2:2:1 ratio to receive OnabotA X [REDACTED] [REDACTED] or [REDACTED] placebo [REDACTED]. Randomization will be stratified at each investigator site by the investigator-assessed baseline severity of GL at maximum contraction using the AGLSS.

Key Eligibility Criteria:	To be eligible for enrollment, at baseline subjects must have AGLSS scores of moderate or severe GL at maximum contraction (also called frown or furrow) by investigator and subject assessments. The investigator and subject scores must be the same.
Study Drug and Duration of Treatment:	On Day 1, eligible subjects will receive a single, double-blind treatment of OnabotA X [REDACTED] or [REDACTED] placebo. Study drug will be administered as [REDACTED] intramuscular (IM) injections into the corrugator and procerus muscles.
Date of Protocol Synopsis:	07 February 2022

2 INTRODUCTION

2.1 Background and Rationale

Why Is This Study Being Conducted?

OnabotA X is an onabotulinumtoxinA investigational product being developed for the treatment of moderate to severe glabellar lines (GL). Hyperfunctional facial lines that develop from repeated facial expression, such as GL, are typically treated by selectively weakening specific muscles with small quantities of botulinum toxin.¹⁻⁵ Botulinum toxins act selectively at the neuromuscular or neuroglandular junction to reversibly block presynaptic acetylcholine release. BOTOX® (onabotulinumtoxinA) was first approved for aesthetic treatment of GL in 2001 and is one of the most common nonsurgical procedures in aesthetic medicine.⁶

2.2 Benefits and Risks to Subjects

OnabotulinumtoxinA is the active drug substance in BOTOX/BOTOX Cosmetic and in OnabotA X; therefore, safety data from prior studies of BOTOX are relevant to the benefit/risk assessment for this first-in-human study of OnabotA X.

The clinical efficacy and safety profile of BOTOX has also been demonstrated in multiple Allergan- and non-Allergan-sponsored clinical trials across several indications, with favorable benefit/risk profiles. In general, adverse reactions occur within the first few days following injection of BOTOX, and while generally transient, may have a duration of several months or, in rare cases, longer.

In a meta-analysis conducted by Brin et al, the most frequently reported adverse events (AEs) among subjects treated for GL with BOTOX [REDACTED] were headache, nasopharyngitis, eyelid sensory disorder, eyelid ptosis, injection site pain, and nausea.⁹ All of these events were mild or moderate in severity, and the incidence decreased with increasing number of treatment cycles.

More detailed information about the known and expected benefits and risks and reasonably expected AEs of OnabotA X may be found in the Investigator's Brochure and the subject's informed consent form (ICF).

For further details, please see findings from completed studies, including safety data in the current OnabotA X Investigator's Brochure.

Considering the coronavirus disease – 2019 (COVID-19) pandemic, the benefit and risk to subjects participating in this study have been re-evaluated. Based on the limited information to date, no additional risk to study subjects is anticipated with the use of OnabotA X.

3 OBJECTIVES AND ENDPOINTS

3.1 Objectives, Hypotheses, and Estimands

Primary

The primary objectives of this study are:

Efficacy: To compare the efficacy of OnabotA X and placebo for the treatment of GL in subjects with moderate to severe GL.

Safety: To evaluate the safety of OnabotA X for the treatment of GL in subjects with moderate to severe GL.

3.2 Primary Endpoint

The primary efficacy endpoint is achievement of ≥ 1 -grade improvement from baseline on the Allergan Glabellar Line Severity Scale (AGLSS) according to investigator assessments at maximum contraction at Day 30.

Estimand attributes of the primary efficacy endpoint are detailed in [Table 1](#).

Table 1. Summary of the Estimand Attributes of the Primary Efficacy Endpoint

Estimand Label	Attributes of the Estimand				
	Treatment	Endpoint	Population	Handling of Intercurrent Events	Statistical Summary
Hypothetical estimand for primary endpoint	OnabotA X or placebo	Achievement of ≥ 1 -grade improvement from baseline on the AGLSS according to investigator assessments at maximum contraction at Day 30	ITT (All randomized)	Missing data will be imputed using multiple imputation.	Difference in response proportions between each active treatment group and placebo, after MI using CMH test stratified by baseline investigator-rated AGLSS at maximum contraction

[figure not shown]
AGLSS = Allergan Glabellar Line Severity Scale; CMH = Cochran-Mantel-Haenszel; ITT = intent-to-treat; MI = multiple imputation; OnabotA X = onabotulinumtoxinA X

3.3 Secondary Endpoints

Secondary Endpoints

- Achievement of None or Mild on the investigator-rated AGLSS assessments at maximum contraction at Day 30
- Responses of Very satisfied or Mostly satisfied on satisfaction with treatment per the FLSQ follow-up version Item 5 at Day 60
- Achievement of ≥ 14 -point psychosocial impact improvement from baseline at Day 30 per the FLSQ Impact domain, among subjects with baseline scores ≥ 14 points

3.4 Additional Efficacy Endpoints

3.5 Safety Endpoints

Safety evaluations include AEs;

3.6 Immunogenicity and Hypersensitivity Sampling

Immunogenicity

Blood samples for immunogenicity testing will be collected from all subjects according to the Study Activities Table ([Appendix D](#)). Collected samples will be processed to yield serum for detection of binding and neutralizing antibodies to OnabotulinumtoxinA.

Hypersensitivity

In suspected cases of anaphylaxis, blood samples should be collected within 2 hours after dosing or as soon as possible. See [Appendix F](#) Operations Manual, Section 3.5 and Section 7.2.

4 INVESTIGATIONAL PLAN

4.1 Overall Study Design and Plan

This is a double-blind, randomized, placebo-controlled, Phase 2 study to assess the safety and efficacy of OnabotA X for the treatment of moderate to severe GL. To be eligible for enrollment, at baseline subjects must have AGLSS scores of moderate or severe GL at maximum contraction (also called frown or furrow) by investigator and subject assessments.

Approximately 280 subjects will be enrolled at approximately 18 sites. Eligible subjects will be randomized in a 2:2:2:1 ratio to receive OnabotA X [REDACTED] or [REDACTED] placebo. Randomization will be stratified at each investigator site by the investigator-assessed baseline severity of GL (AGLSS score) at maximum contraction. Overall study enrollment will be monitored to achieve an approximately balanced [REDACTED] distribution of subjects with investigator-assessed moderate or severe GL at maximum contraction at baseline.

Safety parameters [REDACTED]

[REDACTED] will be monitored (see Operations Manual [[Appendix F](#)] Section 3). At [REDACTED] females of childbearing potential will undergo pregnancy testing. For all subjects, AEs will be collected, whether solicited or spontaneously reported by the subject. Blood samples for immunogenicity testing will be collected [REDACTED]

[figure not shown]
Efficacy will be evaluated based on AGLSS assessed by the investigator and subject, and based on subject responses to FLSQ, [REDACTED]

[REDACTED] Standardized facial photography will be collected at all study visits from Day 1 through study exit.

The schematic of the study is shown in [Figure 1](#). Further details regarding study procedures are in the Operations Manual.

See [Section 5](#) for information regarding eligibility criteria.

Figure 1. Study Schematic

4.2 Discussion of Study Design

Choice of Control Group

A placebo control group is the gold standard for comparative evaluations of safety and efficacy in clinical trials.

Appropriateness of Measurements

Standard statistical, clinical, and laboratory procedures will be utilized in this study. All efficacy and safety-related measurements in this study are appropriate for assessing a novel formulation of a neuromodulator. All clinical and laboratory procedures in this study are standard and generally accepted.

Suitability of Subject Population

The study population will include male and female adults with moderate to severe GL at maximum contraction (also called frown or furrow). To avoid confounding the study results, use of any botulinum neurotoxin for any indication within the 6 months prior to Day 1 is excluded, and washout from prior facial aesthetic treatments is required as described in the eligibility criteria.

Selection of Doses in the Study

There is growing evidence from clinical practice and within published literature that the use of higher doses of onabotulinumtoxinA for facial aesthetic indications, namely treatment of the GL area, provides longer durability of therapy benefit with no deleterious change to the overall product safety profile.¹⁰⁻¹² A sustained clinical benefit [REDACTED] was observed for up to 4 months when the GL area was treated with the approved dose [REDACTED]. Thus, the evaluation of OnabotA X at doses equal to and greater than the approved label dose for GL [REDACTED] is justifiable to evaluate whether this formulation at equal or higher doses might meaningfully extend the time to loss of patient benefit of the aesthetic effect.

5 STUDY ACTIVITIES

5.1 Eligibility Criteria

Subjects must meet all of the following criteria in order to be included in the study. Anything other than a positive response to the questions below will result in exclusion from study participation. Screen failures can occur during the screening period up to the point prior to randomization on Day 1.

Rescreening is not allowed for individuals who do not meet key safety or efficacy Eligibility [REDACTED]. Any attempt to rescreen a subject must only occur after agreement with the sponsor.

Consent

- 1. Subject must voluntarily sign and date an informed consent approved by an independent ethics committee (IEC)/institutional review board (IRB), prior to the initiation of any screening or study-specific procedures.

Demographic and Laboratory Assessments

- 2. Adult male or female, at least 18 years old at the time of ICF signature.
- 3. No clinically significant abnormal values for hematology, chemistry, or urinalysis at screening.

- ✓ [REDACTED]
- ✓ [REDACTED]
- ✓ [REDACTED]
- ✓ 7. Subject is willing and able to comply with procedures required in this protocol.

Disease/Condition Activity

- ✓ 8. Subject has moderate or severe GL at maximum frown [REDACTED]

Subject History

[figure not shown]
[figure not shown]
- ✓ 9. No history of known immunization to any botulinum toxin serotype.
- ✓ 10. No history of known hypersensitivity to any botulinum toxin serotype, [REDACTED] or any other constituents of the study drug or its excipients, and/or other products in the same class.
- ✓ [REDACTED]
- ✓ [REDACTED]
- ✓ 13. No presence or history of any medical condition that may place the subject at increased risk following exposure to OnabotA X or interfere with the study evaluation, including:
 - Diagnosed myasthenia gravis, Lambert-Eaton syndrome, amyotrophic lateral sclerosis, or any other significant disease that might interfere with neuromuscular function
 - Facial nerve palsy
 - Infection or dermatological condition at the site of study drug injection

[figure not shown]
[figure not shown]
A horizontal bar chart showing the percentage of students in each grade level who are not in a math club. The y-axis lists grade levels from 6th to 12th. The x-axis represents the percentage from 0% to 100%. Bars are black with white outlines. A legend in the top left corner shows a green checkmark icon.

Grade Level	Percentage
6th	95%
7th	94%
8th	96%
9th	93%
10th	94%
11th	95%
12th	96%

Contraception

A horizontal bar with a green checkmark icon on the left side, indicating a completed task.

✓  

✓  

Concomitant Medications

Two large black rectangular redaction boxes are positioned side-by-side. Each box has a small green circular icon with a white checkmark in the top-left corner. The boxes are set against a white background.

5.2 Contraception Recommendations

Contraception Requirements for Females

Subjects must follow [REDACTED] contraceptive guidelines [REDACTED]:

- Females, Non-Childbearing Potential

Contraception recommendations related to use of concomitant therapies prescribed should be based on the local label.

5.3 Prohibited Medications and Therapy

In addition to the medications listed in the eligibility criteria, no other facial cosmetic procedures or treatments are to be performed throughout the duration of the study. [REDACTED]

During the study, all other investigational drugs are prohibited.

5.4 Prior and Concomitant Therapy

Any medication or vaccine (including over-the-counter or prescription medicines, vitamins, and/or herbal supplements) that the subject is receiving at the time of enrollment or receives during the study must be recorded from 30 days prior to study drug administration through study exit. See below for details on special handling for the COVID-19 vaccine.

The use of any medication during the study (including prescription or over-the-counter medication, vitamins, and/or herbal supplements) is to be recorded on the subject's eCRF at each visit along with the reason the medication is taken, dates of use, and dosing regimen. Concurrent procedures will also be collected at each visit. Study site personnel must notify the sponsor immediately if a subject uses a concomitant medication or has a concurrent procedure that is prohibited per protocol (see Section 5.3). Subjects who use prohibited concomitant medications or have a prohibited concurrent procedure may be discontinued at the discretion of the investigator or sponsor. Concomitant medications and concurrent procedures will be tabulated and listed.

Non-live vaccines may be used during screening or treatment periods, if not contraindicated or medically inappropriate. When possible, study drug should be given at least \pm 7 days from vaccine administration.

Systemic and topical hormones and their derivatives (i.e., sex steroids - androgens, estrogens, progesterone) should be maintained throughout study period to avoid changes in skin, including but not limited to:

- Oral birth control
- IUDs/implants/injections
- Oral supplements including testosterone & estrogens and their derivatives, dehydroepiandrosterone (DHEA), etc.
- Topicals (anywhere on the body) including testosterone & estrogens and their derivatives, DHEA, etc.

Subjects must maintain their standardized skin care regimen throughout the study period.

Any questions regarding concomitant or prior therapy should be raised to the AbbVie non-emergency contact. Information regarding potential drug interactions with OnabotA X can be located in the OnabotA X Investigator's Brochure.

Subjects must be able to safely discontinue any prohibited medications as described in the eligibility criteria. Subjects must be consented for the study prior to discontinuing any prohibited medications for the purpose of meeting study eligibility.

COVID-19 Pandemic-Related Vaccination Guidance

[REDACTED]

[REDACTED]

[REDACTED]

[REDACTED]

[REDACTED]

5.5 Withdrawal of Subjects and Discontinuation of Study

A subject may voluntarily withdraw or be withdrawn from the study at any time for reasons

[REDACTED]

[REDACTED]

[REDACTED]

[REDACTED]

[REDACTED]

[REDACTED]

For subjects to be considered lost to follow-up, reasonable attempts must be made to obtain information on the subject's final status. At a minimum, 2 telephone calls must be made and 1 certified letter must be sent and documented in the subject's source documentation.

AbbVie may terminate this study prematurely, either in its entirety or at any site. The investigator may also stop the study at his/her site if he/she has safety concerns. If AbbVie terminates the study for safety reasons, AbbVie will promptly notify the investigator.

COVID-19 Pandemic-Related Acceptable Protocol Modification

During the COVID-19 pandemic, it has been necessary to employ mitigation strategies to enable the investigator to ensure subject safety and continuity of care. Acceptable mitigation strategies are identified and included in the Operations Manual in [Appendix F](#), in Section 2 and Section 3.

The investigator should contact the sponsor's non-emergency medical contact before discontinuing a subject from the study for a reason other than described in the protocol, to ensure all acceptable mitigation steps have been explored.

[figure not shown]
5.6 Follow-Up After Subject Discontinuation of Study Drug or from Study

To minimize missing data for efficacy and safety assessments, subjects who prematurely discontinue study drug treatment on Day 1 should continue to be followed for all regularly scheduled visits, unless subjects have decided to discontinue the study participation entirely (withdrawal of informed consent). Subjects should be advised on the continued scientific importance of their data even if they discontinue treatment with study drug early.

If a subject prematurely discontinues study participation (withdrawal of informed consent), the procedures outlined for the Premature Discontinuation visit should be completed as soon as possible, preferably within 2 weeks. In addition, if subject is willing, a 30-day follow-up phone call after the last dose of study drug may be completed to ensure all treatment-emergent AEs/serious adverse events (SAE) have been resolved.

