5.7 Study Drug

[figure not shown]
All subjects will receive OnabotA X or Placebo prepared at the investigational site [REDACTED] administered on Day 1 (Baseline).

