Important Medical Event Requiring Medical or Surgical Intervention to Prevent Serious Outcome	An important medical event that may not be immediately life-threatening or result in death or hospitalization, but based on medical judgment, may jeopardize the subject and may require medical or surgical intervention to prevent any of the outcomes listed above (i.e., death of subject, life threatening, hospitalization, prolongation of hospitalization, congenital anomaly, or persistent or significant disability/incapacity). Additionally, any elective or spontaneous abortion or stillbirth is considered an important medical event along with any suspected transmission of an infectious agent via a medicinal product if no other serious criterion is applicable. Examples of such events include allergic bronchospasm requiring intensive treatment in an emergency room or at home, blood dyscrasias or convulsions that do not result in inpatient hospitalization, or the development of drug dependency or drug abuse.

All AEs reported from the time of study drug administration will be collected for at least 30 days or until the last follow-up visit, whichever is longer, whether solicited or spontaneously reported by the subject.

In addition, study procedure-related serious and nonserious AEs will be collected from the time the subject signs the study-specific informed consent.

AbbVie will be responsible for SUSAR reporting for the IMP in accordance with global and local requirements.

Possible Distant Spread of Toxin

Possible distant spread of toxin (PDSOT) is defined as a possible pharmacologic effect of botulinum toxin at sites noncontiguous and distant from the site of injection. Utilizing a standardized methodology to assess for PDSOT, Medical Dictionary for Regulatory Activities (MedDRA) preferred terms (PTs) that may be associated with botulinum toxin effects have been prospectively identified (see the statistical analysis plan [SAP] for a complete list of these PTs). AEs reporting any of these terms will be medically reviewed on a regular basis throughout the study and will be summarized in the clinical study report.

Adverse Event Severity and Relationship to Study Drug

The investigators will rate the severity of each AE as mild, moderate, or severe.

The investigator will use the following definitions to rate the severity of each AE:

Mild	The AE is transient and easily tolerated by the subject.

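### The optional safety call after withdrawal of consent is timed from the single Day 1 dose, so its date has already passed for any withdrawal after Day 31 of a 270-day study

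*Protocol*

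**What the plan says.** Protocol Section 5.6 separates two groups. Subjects who only stop study drug on Day 1 stay on all scheduled visits. Subjects who leave the study by withdrawing consent are asked to attend a Premature Discontinuation visit, preferably within 2 weeks. In addition, if the subject agrees, "a 30-day follow-up phone call after the last dose of study drug may be completed". The purpose given for the call is "to ensure all treatment-emergent AEs/serious adverse events (SAE) have been resolved".

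Four other places bear on the timing:

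- **Dosing.** The Protocol Synopsis states: "On Day 1, eligible subjects will receive a single, double-blind treatment". Protocol Section 5.7 also places administration on Day 1, and SAP Section 2.1 describes the treatment as a single dose.
- **Length.** The Synopsis states: "This is a 270-day, double-blind, randomized, placebo-controlled, Phase 2 study".
- **Duration of reactions.** Protocol Section 2.2, speaking of the parent product, says that reactions mostly arise in the first few days and are generally transient, but "may have a duration of several months or, in rare cases, longer".
- **Collection of adverse events.** Under Protocol Section 6.1, events reported from study drug administration "will be collected for at least 30 days or until the last follow-up visit, whichever is longer".

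**The concern.** Counting a safety call from the last dose suits a repeat-dose study, where the last dose usually falls close to the time a subject leaves. Here the last dose is also the first. The call date is therefore fixed near the start of follow-up and bears no relation to when the subject withdraws.

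Protocol Section 7.5 defines treatment-emergent events by onset after the first dose and shows no end cut-off. An event that begins on Day 100 is treatment-emergent, and a call due at about Day 31 cannot establish that it resolved.

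At stake is the completeness of outcome data for events still open when a subject who withdraws consent is last seen. Safety is a primary objective, and Section 2.2 calls the study first-in-human for this formulation, so a planned safety contact should be able to do what it is planned for.

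**Working it through.** The plan states no calendar day for the call, so there is no figure to reproduce. The check is calendar arithmetic.

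**Inputs**

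- Dose day: Day 1 (Synopsis; Protocol Section 5.7)
- Call interval: 30 days after the last dose (Protocol Section 5.6)
- Study length: 270 days (Synopsis)
- Premature Discontinuation visit: preferably within 14 days of withdrawal (Protocol Section 5.6)

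**Call day.** Dose day + 30 = 1 + 30 = Day 31. If the dose day were numbered 0, this would be Day 30; the conclusion is the same.

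**Withdrawals for which the date has passed.** For withdrawal on day *w*, the date has passed if *w* > 31. That covers Days 32 to 270: 270 − 31 = 239 days, and 239/270 = 88.5% of study days. This is a share of calendar days, not of withdrawals.

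**Examples.** The last column is for illustration only and shows the same 30 days counted from withdrawal.

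| Withdrawal day *w* | Call due | Call minus withdrawal (days) | Discontinuation visit by (*w* + 14) | *w* + 30 |
|---|---|---|---|---|
| 10 | Day 31 | +21 | Day 24 | Day 40 |
| 31 | Day 31 | 0 | Day 45 | Day 61 |
| 60 | Day 31 | −29 | Day 74 | Day 90 |
| 120 | Day 31 | −89 | Day 134 | Day 150 |
| 240 | Day 31 | −209 | Day 254 | Day 270 |

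**When the call adds a contact later than the visit.** If the visit takes the full 2 weeks, the call comes after it only when *w* + 14 < 31, that is, for withdrawals on Days 1 to 16. If the visit takes place on the day of withdrawal, the condition is *w* < 31, that is, Days 1 to 30. So the call extends follow-up beyond the visit for withdrawals on the first 16 to 30 days of 270 (5.9% to 11.1% of study days).

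**Against the stated duration of reactions.** The protocol does not define several months. Assuming 3 to 6 months, a reaction starting soon after dosing could run to about Day 92 to Day 183, well beyond Day 31. So even for a very early leaver, a Day 31 call may come too soon to confirm resolution of a long-lasting event.

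**What remains covered.** Under Protocol Section 6.1, collection runs to the later of 30 days and the last follow-up visit. For a Day 60 withdrawal with the visit on Day 74, events are collected to Day 74. The visible text sets no contact after that.

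**The case against.** The best defence is that the call merely completes the 30-day minimum in Protocol Section 6.1 for someone who leaves before Day 31. For later leavers that minimum is already met and the call is simply not needed. The reading is coherent and fits the optional wording. It does not fit the stated purpose, which is resolution of all treatment-emergent events and not completion of a 30-day window. If the shorter aim was meant, the purpose clause promises more than the call can deliver.

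Several limits on the point do stand:

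- A reader might infer that late leavers get no safety follow-up. They do: the Premature Discontinuation visit remains, and events are collected up to it.
- A reader might infer that outcomes of open events will be left unknown. The documents do not establish this. The wording of Section 6.1 allows longer collection and does not say that recorded events stop being updated. Parts of Protocol Section 5.5 are redacted, and the Operations Manual, which Section 6.1 cites for reporting of serious events, is not among the documents. A rule on following events to resolution may sit there.
- A reader might infer that the Phase 3 dose recommendation is affected. The visible SAP safety tables (Section 10.2) summarise occurrence by system organ class, preferred term and maximum severity; no analysis of event duration or resolution is visible. The recommendation comes from interim review by the data monitoring committee (SAP Sections 12.0 and 12.1), and the timing of that review is redacted. Withdrawal driven by dose is also not documented.
- Long reactions are described as possible, not typical, so open events in late leavers may be few.

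**Conclusion.** The timing in Protocol Section 5.6 does not fit the single-dose design or the call's own stated purpose. The call is due at about Day 31, and for withdrawals on Days 32 to 270 (239 of 270 days) that date has already passed. This follows from the protocol's own figures and needs no assumption beyond counting the dose day as Day 1.

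The practical gap is narrow: a missing later contact, in the visible text, for events still open at the Premature Discontinuation visit. It concerns subjects who withdraw consent, have an open event at that visit and are willing to be called. It would be tempting to turn 88.5% of days into a number of subjects, but the documents give no withdrawal rate, no timing of withdrawals and no rate of open events at exit, so any headcount would be guesswork. Subjects lost to follow-up are handled separately in Section 5.5.

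The efficacy analyses are unaffected. The point is worth correcting because the contact is already planned and is easily made useful. If the Operations Manual already has an outcome follow-up rule, the practical gap may be closed, but the wording of Section 5.6 would still need to be reconciled with it.

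**What to change.** Reconcile Protocol Section 5.6 with the Synopsis and Section 5.7 (single Day 1 dose), Section 2.2 (possible duration of reactions) and Section 6.1 (collection window):

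1. In Section 5.6, time the optional call from the Premature Discontinuation visit, or from last contact if that visit does not take place, instead of from the last dose.
2. In Section 6.1, state that outcomes of events open at that visit may be recorded up to the call.
3. Check both changes against the Operations Manual and the redacted parts of Section 5.5, so that only one rule applies.

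The call stays optional and the limits set by consent are unchanged. Treatment, visits for continuing subjects and the analyses are not altered.

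The cost is a short amendment, a later call for each willing subject, and a slightly longer contact period for a few early leavers. The yield is limited in turn, because it depends on the willingness of people who have already withdrawn consent.
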